### **3.6. Adjustments for Covariates**

No formal statistical analyses that adjust for possible covariate effects are planned.

### **3.7. Multiple Comparisons/Multiplicity**

Multiplicity is not of concern for this study with a descriptive interpretation.

### **3.8. Subpopulations**

For purposes of the summary tabulations, data may be stratified by age group ( $\geq 6$  to  $< 12$  years old,  $\geq 12$  to  $< 18$  years old,  $\geq 18$  years old).

Additionally, data may be stratified by genetic obesity disorder.

### **3.9. Withdrawals, Dropouts, Loss to Follow-up**

Patients will be informed that they have the right to withdraw from the study at any time for any reason, without prejudice to their medical care. The Investigator also has the right to withdraw patients from the study for reasons such as:

- AEs, which in the opinion of the Investigator, justify treatment or study withdrawal.
- Non-adherence to the study drug regimen or protocol requirements.
- Non-compliance with instructions or failure to return for follow-up.

The patient's reason for and date of withdrawal from the study are to be recorded in the case report form (CRF). Any patient withdrawing from the study will complete the Early Termination Visit, if possible.

### **3.10. Missing, Unused, and Spurious Data**

In general, no missing data will be imputed for this study and analyses will be carried out on all available data. Imputation of missing questionnaire data will be applied for the derivation of summary scores, dependent on the questionnaire and imputation rules of the questionnaire. [REDACTED]

When tabulating AE data, partial dates will be handled as follows:

- If the day of the month is missing, the onset day will be set to the first day of the month unless it is the same month and year as study treatment. In this case, in order to conservatively report the event as treatment-emergent, the onset date will be assumed to be the date of treatment.
- If the onset day and month are both missing, the day and month will be assumed to be January 1, unless the event occurred in the same year as the study treatment. In this case, the event onset will be coded to the day of treatment in order to conservatively report the event as treatment-emergent.
- A missing onset date will be coded as the day of treatment.

For prior and concomitant medications (as defined in [Section 4.4.7](#)), partial start dates will not be imputed, as stop dates determine prior versus concomitant. Partial stop dates will be assumed to be the latest possible date consistent with the partial date.

All data recorded on the CRF will be included in data listings that are placed in the CSR appendices.

If any data is missing at the two key timepoints of Week 14 or Week 26 for any [REDACTED] analysis, the last observation carried forward method will be used to impute observations at those two visits. Any observation carried forward to these visits must have originated in their respective study period (Period 1 for Week 14, Period 2 for Week 26).

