### **4.5.2. Adverse Events**

All AEs will be coded using the MedDRA coding system (Version 24.0 or later) and displayed in tables and data listings by SOC and PT. Adverse events will also be graded using the National Cancer Institute Common Terminology Criteria for AEs (NCI-CTCAE) on a scale of Grades 1 to 5 in which Grade 1 is a mild AE, Grade 2 a moderate AE, Grade 3 a severe AE, Grade 4 a life-threatening or disabling AE, and Grade 5 a fatal AE). Those not listed by CTCAE will be graded as either mild, moderate, or severe.

Analyses of AEs will be performed for those events that are considered treatment-emergent, where treatment-emergent is defined as any AE with onset after the administration of randomized study medication at the start of the Run-in period through the end of the study (at the end of the 3-week follow-up period), any event that was present at baseline (beginning of Run-in period) but worsened in intensity or was subsequently considered drug-related by the Investigator through the end of the study, or any event deemed to be related to study drug exposure.

The number and percentage of patients with any treatment-emergent adverse event (TEAE), with any TEAE assessed by the Investigator as related to treatment (definite, probable, or possible relationship), with any serious TEAE, any serious related TEAE, with any TEAE resulting in study drug withdrawal, with any TEAE leading to death will be summarized by QD/QW treatment group and overall. All TEAE analyses will have separate tabulations for two time frames: the beginning of the randomized, double-blind period (Day 1) to Week 14 and the beginning of the Run-in period through the end of the 3-week follow-up period (end of study). Since visits are not collected for AEs, the dates that each patient started and ended treatment at

each of these periods will be used to compare to the AE start and end dates for each patient in order to subset on the AEs specific to the randomized, double-blind period.

In these tabulations, each patient will contribute only once (i.e., the most related occurrence or the most intense occurrence) to each of the incidence rates in the descriptive analysis, regardless of the number of episodes.

No formal hypothesis-testing analysis of AE incidence rates will be performed.

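### SAP 3.10 sends incomplete AE onset dates to an undefined treatment date or the first of the month, which can put an event in the wrong period of the Day 1 to Week 14 table

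*SAP*

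**What the plan says.** SAP 3.10 has three rules for incomplete AE onset dates.

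- Only the day unknown: "the onset day will be set to the first day of the month unless it is the same month and year as study treatment". For that exception, "the onset date will be assumed to be the date of treatment".
- Day and month both unknown: "the day and month will be assumed to be January 1, unless the event occurred in the same year as the study treatment"; the day of treatment then applies.
- Whole date unknown: "A missing onset date will be coded as the day of treatment".

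The stated purpose is "in order to conservatively report the event as treatment-emergent". The rules do not mention study period, formulation or AE stop date, and no sensitivity analysis is planned.

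SAP 4.5.2 plans every treatment-emergent table for two windows: "the beginning of the randomized, double-blind period (Day 1) to Week 14 and the beginning of the Run-in period through the end" (here, the close of follow-up). It says visits are not collected for AEs, so the treatment dates for "each of these periods will be used to compare to the AE start and end dates for each patient".

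**The concern.** The rules suit a trial with one treatment start. Here (SAP 1.2.1 and Table 1) patients take once-daily (QD) drug in Run-in for 1 to 7 days, start randomized QD or QW treatment on Day 1, all go to open-label QW at Week 14 (Day 92), and all return to QD at Week 27 (Day 183). SAP 3.10 does not say which start the date of treatment means.

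The rest of the plan does not settle it. SAP 3.4 takes the safety baseline before the first dose in this study, which is the Run-in dose. SAP 4.5.2 starts treatment emergence at Run-in, although it calls that drug randomized. Protocol 8.8.11.1 also counts events from the start of Run-in. But SAP 3.2 calls the day of first dose Day 1, and Table 1 puts Day 1 at randomization.

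At stake is the Day 1 to Week 14 table, the only planned AE table confined to the randomized, blinded comparison. QW safety is the secondary objective. An imputed date can decide whether an event is in that table, and two programmers could build different versions from the same text.

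**Working it through.** The plan gives no figure on this point, so there is none to reproduce.

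**Inputs.** Schedule days: 13×7+1 = 92, 26×7+1 = 183 and 29×7+1 = 204, which match Table 1. The double-blind and open-label periods are therefore 91 days each, and follow-up is Days 183 to 204, or 22 days. Assumptions, not in the documents: onset uniform over study days, Day 1 uniform over a 365-day year, and the month of treatment meaning the month of the anchor dose.

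**Day missing, event after the Week 14 switch.** The event moves back before the switch if it falls in the switch's calendar month and the switch is not on the 1st. For a month of L days, summing the days from the switch to month end over switch days 2 to L gives L(L−1)/2. Over the year this is 7×465 + 4×435 + 378 = 5,373. Per switch date: 5,373/365 = 14.7 days. Share of open-label events: 14.7/91 = **16.2%**. The anchor does not enter.

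**Day missing, double-blind event, Run-in anchor.** The same sum applies to Day 1. An event in Day 1's calendar month goes either to the Run-in dose or to a first of the month that precedes Day 1. The result is again 14.7/91 = **16.2%**, for a 1-day or a 7-day Run-in. With a Day 1 anchor it is 0%.

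**Day missing, QD follow-up event.** The same sum with each run capped at 22 days gives 7×429 + 4×407 + 363 = 4,994. Then 4,994/365 = 13.7 days, and 13.7/22 = **62.2%** move back into the open-label QW period.

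**Day and month missing, Run-in anchor.** A double-blind event stays in place only if January 1 falls in the double-blind period on or before it: (91×92/2)/(365×91) = 4,186/33,215 = 12.6%, so 87.4% move to Run-in. For open-label events, 12.6% stay, 91×91/33,215 = 24.9% go to double-blind, and the remaining 62.5% go to Run-in.

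Enumerating every Day 1 and every onset day gives the same results:

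| Missing | True period | Run-in dose as anchor | Day 1 as anchor |
|---|---|---|---|
| Day | Run-in | none leave | 87% (7-day Run-in) to 97% (1-day) to double-blind |
| Day | Double-blind | 16.2% to Run-in | none leave |
| Day | Open-label QW | 16.2% to double-blind | 16.2% to double-blind |
| Day | QD follow-up | 62.2% to open-label QW | 62.2% to open-label QW |
| Day, month | Double-blind | 87.4% to Run-in | none leave |
| Day, month | Open-label QW | 62.5% to Run-in, 24.9% to double-blind | 87.4% to double-blind |
| Whole date | Any | 100% to Run-in | 100% to double-blind |

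For scale, Run-in is 1/205 = 0.5% to 7/211 = 3.3% of the days from first dose to Day 204.

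**Example.** Run-in starts 25 February, Day 1 is 4 March, and the switch is 3 June. An event on 20 March recorded only as March becomes 1 March (Run-in) with the Run-in anchor, or 4 March (double-blind) with the Day 1 anchor. An event on 20 June recorded only as June becomes 1 June under both, which is before the switch. If the patient was randomized to QD, an event on active QW enters the QD column.

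**The case against.** A reader might infer that the rule shifts events in one direction, from QW to QD and out of the double-blind window. The documents do not support that. Leaving the window depends on the Run-in anchor, which is inferred. With a Day 1 anchor, events move in. Open-label events moved back before Week 14 also enter the double-blind window, and those of QW-randomized patients stay in the QW column. QD follow-up events move into the QW period. A Run-in fallback would remove events from both arms, so no direction for the randomized contrast follows.

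Exposure is also limited. SAP 3.5 groups patients by randomized sequence, so on that grouping the whole-study table hardly changes when an event crosses Week 14. No separate open-label AE table is planned. Injection site evaluations (SAP 4.5.3) are summarized by visit and treatment received, not by imputed AE onset. SAP 4.5.2 compares end dates as well as start dates, so an event imputed to Run-in that ends later is not certainly dropped. AEs are assessed weekly up to Week 14, so poorly dated onsets there should be rare. The trial is descriptive, with no hypothesis tests.

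All of this stands and limits the size of the point. It leaves the anchor undefined and does not stop period misallocation, which occurs under either reading. The same section restricts last-observation-carried-forward values to their own study period, but gives AE onsets no such protection.

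**Conclusion.** The concern holds for the Day 1 to Week 14 table. With the Run-in anchor, the better-supported reading, all wholly undated events and about 16% of double-blind events lacking the day are placed in Run-in by onset date. With either anchor, about 16% of open-label QW events lacking the day are placed before Week 14.

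The percentages rest on the uniform-onset assumption and apply only to incompletely dated events. The documents give no frequency for these, so the absolute effect is unknown and probably small. With about 30 patients randomized 1:1, one patient is 1/15, or about 7 percentage points of an arm. That much moves only if the event is the patient's sole contribution to the row, because each patient counts once. If the month of treatment were read as any month with dosing, all events lacking the day while on dosing would go to the anchor date, which is worse. The change should be made, but the point does not threaten the trial's conclusions.

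**What to change.** In SAP 3.10:

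1. Name Day 1 (first randomized dose) as the fallback whenever the recorded date parts and AE stop date allow onset on or after Day 1. Use the first Run-in dose only when they do not.
2. Restrict every imputed onset to dates consistent with the recorded parts and the stop date. Protocol 9.3.3 already lists resolution dates.
3. For events whose possible onset spans Day 1, the Week 14 switch or the Week 27 return to QD, report the count and show the Day 1 to Week 14 table under both allocations.

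Do not default to the switch date in the switch month. By the same sum, an average of 14.7 of the 91 double-blind days precede the switch in its month, so about 16% of double-blind events lacking the day would be pushed into the open-label period: the mirror error.

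The cost is SAP wording, a few lines of programming and one small sensitivity table, with no new data. The downside is that some true Run-in events may be counted as double-blind. It should be settled before unblinding.

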### **3.11. Visit Windows**

It is expected that all visits should occur according to the protocol schedule. All data will be tabulated per the evaluation visit as recorded on the CRF even if the assessment is outside of the visit window. If the evaluation visit is missing in the database but there are data from an unscheduled or additional visit that is within the visit window, the data from the unscheduled or additional visit will be used in data summaries. All available data will be listed for each patient.

### **3.12. Interim Analyses**

No unblinded interim analysis is planned. Blinded interim analyses may be conducted during the course of the trial to facilitate scientific monitoring and business needs.

## 4. STUDY ANALYSES

### 4.1. Patient Disposition

Patient disposition will be tabulated and include the number of patients screened, randomized, treated in total, in the QD setmelanotide group, in the QW setmelanotide group (see [Section 3.5](#)), in each patient population for analysis, who discontinued prior to completing the study and reason(s) for early study discontinuation, who discontinued prior to completing the treatment and reason(s) for early treatment discontinuation, and the number of patients that have completed the study

A by-patient data listing of study completion information including the reason for premature study withdrawal, if applicable, will be presented.

### 4.2. Demographics, Baseline Characteristics, and Medical History

Demographics and baseline characteristics information will be summarized by QD/QW setmelanotide group for the FAS using the [REDACTED] baseline as well as for the SA set using the safety baseline. No formal statistical comparisons will be performed. Age at baseline as well as baseline height, [REDACTED]

The number and percentage of patients in each age category ( $\geq 6$  to  $< 12$  years old,  $\geq 12$  to  $< 18$  years old,  $\geq 18$  years old), sex, ethnicity, race, and genetically defined deficiency categories will also be presented. Skin type as measured by the Fitzpatrick Classification Scale, which is defined below, will also be summarized:

**Table 2 Fitzpatrick Classification Scale**

Skin Type	Skin Color	Characteristics
I	White; very fair; red or blond hair; blue eyes; freckles	Always burns, never tans
II	White; fair; red or blond hair; blue, hazel, or green eyes	Usually burns, tans with difficulty
III	Cream white; fair with any eye or hair color; very common	Sometimes mild burn, gradually tans
IV	Brown; typical Mediterranean Caucasian skin	Rarely burns, tans with ease
V	Dark Brown; mid-eastern skin types	Very rarely burns, tans very easily
VI	Black	Never burns, tans very easily

Source: Fitzpatrick TB. Soleil et peau. J Med Esthet. 1975;2:33034.

Demographic and baseline data for each patient will be provided in data listings.

The patient's history of childhood obesity and previous weight loss efforts will be collected. This medical history will be summarized in a table by System Organ Class (SOC) and Preferred Term (PT) frequencies for the SA set. This data will also be provided in a data listing.

[REDACTED]

#### **4.4. Pharmacokinetic Evaluations**

Primary [REDACTED] analysis will be conducted using the PKAS.

##### **4.4.1. Primary [REDACTED] Analysis**

For the primary [REDACTED] endpoint, the PK profile of the 2 formulations of setmelanotide will be characterized and the steady-state PK parameters ( $C_{max}$ ,  $T_{max}$ ,  $C_{trough}$ ,  $AUC_{0-tau}$ ) will be summarized by dose level and prior treatment regimen (QW or QD) during the double-blind phase of the study using descriptive statistics including n, mean, standard deviation,

geometric mean, minimum, median, maximum, % coefficient of variation (CV), geometric mean CV, and 95% confidence intervals (CIs).

A separate tabulation will be created for the same analysis by subgroup (age category and genetic subgroup).

## **4.5. Safety Analyses**

Safety analyses will be conducted using the SA Set.

### **4.5.1. Drug Exposure**

Drug exposure will be summarized by QD/QW treatment group across the entire length of the study. The number of doses administered, total dose received in mg, treatment duration in weeks, and percentage of dosing compliance will be summarized using descriptive statistics (N, mean, SD, median, minimum, maximum, and 95% confidence intervals). Treatment duration will be defined in weeks as  $(\text{date of last dose} - \text{date of first dose} + 1) / 7$ . Dosing compliance percentage will be defined as  $([\text{number of doses administered}] / [\text{duration of treatment in days}]) * 100$  for QD treatment and  $([\text{number of doses administered} * 7] / [\text{duration of treatment in days}]) * 100$  for QW treatment. A by-patient listing for dosing will be created.

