7.4. Treatment Compliance

Accountability for the study drug (including placebo) at the trial site is the responsibility of the Investigator. The Investigator will ensure that the study drug is used only in accordance with this protocol. Where allowed, the Investigator may choose to assign drug accountability responsibilities to a pharmacist or other appropriate individual. Drug accountability records indicating the delivery date to the site, inventory at the site, use by each patient, return of all used study drug to the trial center, and return to the Sponsor (or disposal of the drug, if approved by the Sponsor) will be maintained by the clinical site. Reasons for departure from the expected dispensing regimen must also be recorded. The Sponsor or its designee will review drug accountability at the site during monitoring visits.

Compliance with dosing will be monitored throughout the trial by having the patient/caregiver capture dosing in an electronic diary, and by accounting for vials dispensed and returned (used and partially used).

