The patient will have a Run-in Period of 1 day to 1 week on QD setmelanotide at the dose they received in the LTE study. The first day of the Run-in Period (Visit 2) should coincide with the patient's last visit in the LTE study to avoid an interruption of treatment. The first dose of QD setmelanotide as part of the RM-493-037 study will occur in clinic on the first day of the Run-in Period. On the first day of the Run-in Period, patients will have serial blood samples taken for measurement of setmelanotide concentrations (QD formulation) and 24-hour PK profiles (including optional timepoint at 12 hours after dosing) will be performed.

On Day 1 (Visit 3) patients will be randomized 1:1 to receive either QD or QW setmelanotide. Patients who received QD setmelanotide at a dose of 2 mg at the time of study entry will be

[figure not shown]
randomized to receive either QD setmelanotide 2 mg or QW setmelanotide at a dose of 20 mg, whereas patients who were on QD setmelanotide at a dose of 2.5 mg will be randomized to receive either QD setmelanotide 2.5 or QW setmelanotide at a dose of 25 mg, and finally patients who were on QD setmelanotide at a dose of 3 mg will be randomized to receive either QD setmelanotide 3 mg or QW setmelanotide at a dose of 30 mg. Study medication will be administered in a double-dummy fashion in order to maintain the double blind. Patients will receive the first QW dose on Day 1 of the randomized treatment period (Visit 3). The randomization will be stratified by age group.

- Patients randomized to QW setmelanotide will receive blinded QW setmelanotide and QD placebo injections until the Week 14 visit (i.e., completion of 13 weeks of blinded dose administration). Starting with Week 14, patients will continue with open-label QW injections of setmelanotide during the 13-week non-randomized phase of the study.
- Patients randomized to QD setmelanotide will receive blinded QD setmelanotide and QW placebo injections until the Week 14 visit (i.e., completion of 13 weeks of blinded dose administration). Starting with Week 14, patients will continue with open-label QW injections of setmelanotide during the 13-week non-randomized phase of the study.

For the 3-week Follow-up Period, all patients will return to their allocated run-in medication of QD setmelanotide to prepare for re-enrollment into Study RM-493-022 or to resume the QD formulation in some other way.

The study design is depicted graphically in [Figure 1](#).

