**Figure 1 Study Design Schematic**

### 1.2.2. Randomization Methodology

Patients will be randomized 1:1 on Day 1 (Visit 3) to treatment with either QD or QW setmelanotide, stratified by age group ( $\geq 18$  years old;  $\geq 12$  to  $< 18$  years old;  $\geq 6$  to  $< 12$  years old). The study staff will use an interactive response technology (IRT) system to obtain the randomization number for each patient. To maintain the blind during the 13-week randomized treatment period, all patients will receive placebo injections (from the QD formulation or from the QW formulation) in addition to the setmelanotide injections in a double-dummy fashion. Randomization numbers will not be re-used once assigned. Please refer to the official randomization plan for more details. No randomization or blinding will be done for the 13-week open-label phase or for the 3-week QD follow-up phase.

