#### **3.4. Baseline Definitions**

For all [REDACTED] analyses, baseline will be defined as the following: the last value prior to randomization in the 13-week double-blind period.

For safety parameters including key laboratory (e.g., hematology and chemistry) data, the last value obtained prior to the first dose of setmelanotide or placebo in RM-493-037 will be used as the baseline. For the C-SSRS analysis, the baseline assessment that was collected at the beginning of the index study [REDACTED] should continue to be used as the baseline for this study.

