### **3.5. Methods of Pooling Data**

There will be two groups pooled to categorize the setmelanotide treatments so that differences between QD/QW can be easily seen: QW and QD. The QD group includes those patients who were randomized to QD setmelanotide in the randomized double-blind treatment period (Period 1) and QW setmelanotide in the open-label period (Period 2). The QW group includes those patients randomized to QW setmelanotide in the randomized double-blind treatment period (Period 1) and in the open-label period (Period 2).

Summary tabulations may be pooled across genetic obesity disorder populations as available.

In certain cases, tabulations will be stratified by age group ( $\geq 6$  to  $< 12$  years old,  $\geq 12$  to  $< 18$  years old,  $\geq 18$  years old). All of these patients must have participated in the extension study, RM-493-022.

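### SAP 4.5.1 does not give 100% weekly compliance for full adherence: it gives 107.1% or 103.4% on weekly-dose dates, and 43–45% or 86–89% on whole-study dates

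*SAP*

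**What the plan says.** SAP 4.5.1 sets the scope: "Drug exposure will be summarized by QD/QW treatment group across the entire length of the study". It then gives one definition of duration: "Treatment duration will be defined in weeks as" the last dose date minus the first dose date plus one, divided by 7. Two compliance percentages follow. For QD treatment it is doses divided by days of treatment. For QW treatment it is doses times 7 divided by days of treatment. Both use the same duration, and neither says whether its dates belong to the regimen, the period or the whole study.

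No completer takes only one regimen. SAP 3.5 defines the QD group as patients "randomized to QD setmelanotide in the randomized double-blind treatment period (Period 1) and QW setmelanotide in the open-label period (Period 2"). SAP 1.2.1 puts all patients on daily drug during run-in, and adds: "For the 3-week Follow-up Period, all patients will return to their allocated run-in medication of QD setmelanotide".

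The double-blind period is double-dummy: "Patients randomized to QW setmelanotide will receive blinded QW setmelanotide and QD placebo injections until the Week 14 visit". The later phases are not: "No randomization or blinding will be done for the 13-week open-label phase or for the 3-week QD follow-up phase". SAP 4.5.1 does not say whether a placebo injection counts as a dose. The only nearby wording, in the safety baseline rule of SAP 3.4, does count placebo when fixing the first dose: "the last value obtained prior to the first dose of setmelanotide or placebo in RM-493-037 will be used as the baseline".

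Protocol 7.4 gives no formula that would settle this. It says how the data are collected: "Compliance with dosing will be monitored throughout the trial by having the patient/caregiver capture dosing in an electronic diary", together with vial counts.

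**The concern.** A compliance percentage should read 100 when every scheduled dose is taken, and should fall when a dose is missed. The QW formula credits each weekly dose with seven days, but the duration stops on the day of the last dose. The final dose therefore adds seven days to the numerator and one to the denominator. The alternative, whole-study dates, puts weeks spent on the other regimen into the denominator.

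The consequences on weekly-dose dates are these:

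- The excess depends on the number of doses. Patients who stop early score highest, and two equally adherent groups differ because one has 13 weekly doses and the other 26.
- Missing the last dose raises the score.
- The QD formula, applied to daily dates within one period, gives exactly 100% for full adherence (91/91). The comparison therefore favours QW by construction. Protocol 3.1 and 3.2 put forward better compliance as a reason for the weekly product, so this table is likely to be read for that purpose.

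Whole-study dates err the other way and would make fully adherent patients look non-compliant. Either way, SAP 4.5.1 attaches means, standard deviations and 95% confidence intervals to the values.

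**Working it through.** **Inputs.** The calendar comes from the schedule of assessments (SAP Table 1): first double-blind weekly dose on Day 1, first open-label weekly dose on Day 92, daily dosing restarted on Day 183, end of study on Day 204. Each 13-week period holds 13 weekly doses. SAP 1.2.1 gives a run-in of 1 to 7 days. I assume 21 or 22 daily doses in follow-up, with the last on Day 203 or 204.

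**The plan's own figure.** The documents state no compliance percentage. The protocol synopsis gives about 30 weeks of total treatment. First run-in dose to Day 204, with no Day 0, is 205 or 211 days, which is 29.3 or 30.1 weeks. The whole-study denominator is therefore read correctly. Allowing for the last dose on Day 203 or 204, it is 1 + 91 + 91 + 21 = 204 to 7 + 91 + 91 + 22 = 211 days.

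**Reading 1: duration from first to last weekly dose.** On-time weekly doses numbering n span 7(n − 1) + 1 = 7n − 6 days, so full adherence scores 7n/(7n − 6), which always exceeds 100%.

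| Case | Calculation | Score | Doses taken / scheduled |
|---|---|---|---|
| 13 of 13 (e.g. open-label, Days 92–176) | 91/85 | 107.1% | 100% |
| 26 of 26 (Days 1–176) | 182/176 | 103.4% | 100% |
| Stops after 4 on-time doses | 28/22 | 127.3% | 100% to that point |
| Stops after 8 on-time doses | 56/50 | 112.0% | 100% to that point |
| Final dose of 13 missed | 84/78 | 107.7% | 92.3% |
| One interior dose of 13 missed | 84/85 | 98.8% | 92.3% |
| Final dose of 26 missed | 175/169 | 103.6% | 96.2% |

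Placebo handling cannot rescue the open-label phase, because no daily placebo is given then.

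**Reading 2: whole-study duration, full adherence.**

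- QW arm, 26 weekly doses in the QW formula: 182/211 = 86.3% to 182/204 = 89.2%.
- QD arm, 13 active weekly doses in the QW formula: 91/211 = 43.1% to 91/204 = 44.6%.
- QD arm, all active doses in the QD formula: (1 + 91 + 13 + 21)/204 = 126/204 = 61.8% to (7 + 91 + 13 + 22)/211 = 133/211 = 63.0%.

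Letting the last dose move with the ±3-day window at the final visit widens the QW-formula limits to 91/214 = 42.5% and 182/202 = 90.1%.

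**Reading 3: double-blind period with placebo.** If the daily placebo injections set the duration (91 days) but are not counted as doses, the QW arm scores 13 × 7/91 = 100.0%. If the weekly placebo injections are counted as doses in the QD arm, that arm scores (91 + 13)/91 = 114.3%. SAP 4.5.1 does not choose between these conventions.

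**The case against.** The strongest reply is that this is under-specification rather than error. SAP 4.5.1 does not say which dates apply, so Readings 1 and 2 are alternatives and at most one set of figures can appear. Period-level dates will exist anyway, because SAP 4.5.2 uses each patient's treatment start and end dates by period for adverse events. On Days 92–182, 13 open-label doses would score 91/91 = 100%.

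It is true that the readings are alternatives, and that 43–45% and 86–89% belong to different arms with nothing between. The period-date argument does not succeed. It belongs to the adverse event tabulation and does not change the first-to-last-dose definition in 4.5.1. In the open-label phase, both ways of applying that definition misstate full adherence.

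Several smaller points stand. The 114.3% and 61.8–63.0% figures need unlikely choices about which injections enter the QD formula. The early-stopping figures are illustrations, since the documents give no expected dropout. SAP 3.4 concerns baseline, so it is weak evidence on counting doses. An interior missed dose still shows as a fall of about 8 points, and the reversal for a missed final dose is only 0.6 points (107.1% to 107.7%).

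On importance, the trial is descriptive and compliance is not an endpoint. SAP 2.2 sets no compliance threshold for the per-protocol set, and the by-patient dosing listing lets true adherence be recovered.

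**Conclusion.** The concern holds. As written, SAP 4.5.1 gives a wrong compliance figure for weekly dosing. Full adherence scores 107.1% (13 doses) or 103.4% (26 doses) on weekly-dose dates. On whole-study dates it scores 43.1–44.6% (QD arm) or 86.3–89.2% (QW arm). No reading of its duration definition gives 100% for weekly dosing throughout the trial.

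The weekly-dose-date figures rest only on the nominal schedule. The whole-study figures also assume a run-in of 1–7 days, 21–22 follow-up doses, and only active weekly doses in the numerator. The damage is limited to the descriptive exposure table, and the primary pharmacokinetic summary is unaffected. This should be corrected before the table is programmed, but it does not threaten the trial's main conclusions.

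**What to change.** Define compliance in SAP 4.5.1 as doses taken divided by doses scheduled, times 100. Calculate it separately for daily and weekly injections within each treatment period, counting scheduled doses to the end of the period or to discontinuation. State whether placebo injections count as doses and whether they set the duration. Full adherence then scores 100%, and any single miss out of 13, including the last dose, scores 12/13 = 92.3%.

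If a duration-based weekly formula is kept, use last weekly dose date minus first weekly dose date plus 7. This gives 91/91 and 182/182 = 100% for full adherence and 84/91 = 92.3% for one interior miss. It still scores a missed final dose as 84/84 = 100%, so the scheduled-dose form is better.

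The cost is SAP wording and programming only, because the dosing diary already records every daily and weekly dose.
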